### **Change in Modified Rankin Scale Score**

The mRS is a 7-point disability scale that assesses the degree of disability in patients with neurological impairment. Possible scores range from 0 (no symptoms at all) up to 6 (death). The higher scores reflect increased disability. Descriptive statistics will be calculated for the change in mRS.

The mean change in mRS score will be analyzed from baseline to every 24 weeks after the baseline visit.

### **Change in Zarit Burden Interview Score**

The ZBI is the measurement to assess caregiver burden. The 22 items ask for the strain caregivers perceive. Responses range from 0 (never) to 4 (nearly always) with maximum score of 88. The higher the total score, the heavier the perceived burden. Descriptive statistics will be calculated for the change in ZBI.

The mean change in ZBI score will be analyzed from baseline to every 24 weeks after the baseline visit.

### **Change in Expanded Disability Status Scale (EDSS) Score**

The EDSS will be assessed on scheduled visits during entire study. The mean change in EDSS scores from baseline to every 24 weeks after the baseline visit will be analyzed.

*Time to EDSS worsening based on the definition for PDR is estimated with a Cox regression with treatment group, baseline ARR and geographical region as covariates. The hazard ratio and 95% CI for the treatment groups is estimated in this model, the p value is calculated based on the log rank test. In addition, Kaplan-Meier estimate of event-free rates will be provided.*

*These analyses are done for the double-blind period and the combined double-blind and OLE period. When both periods are analyzed together, patients are analyzed as randomized, even if patients randomized to placebo receive satralizumab in the OLE period.*

### **Change in Visual Acuity (Snellen Chart)**

Visual acuity will be measured by a Snellen 20-foot wall chart. The test will be performed monocularly and patients may use their habitual distance glasses or contact lenses.

The same visual acuity testing method is to be employed for all study visits for each patient.

### **Analysis of Secondary Endpoints**

A mixed-effects model repeated measures (MMRM) analysis will be used for the change from baseline in EDSS, SF-36, VAS for pain, FACIT fatigue, mRS, ZBI and EQ-5D scores, as well as visual function testing. The model will include treatment group, protocol-specified visit, treatment-by-visit interaction as fixed effects; the baseline measurements as a covariate; and visit as a repeated measure. *An* unstructured covariance matrix will be assumed in the model.

If the unstructured covariance matrix does not converge, other covariance structure will be used. If treatment-by-visit interaction is not statistically significant, we still keep the full model.

If the normality assumption for the secondary efficacy variable does not hold, generalized estimating equation or generalized linear mixed-effect model analysis will be used. The assessment will be performed prior to unblinding and details will be mentioned in the SAP.

### ***Use of Rescue Medication***

*The use of rescue medication is based on treated clinical relapses. If a patient has at least one treated clinical relapse, then this patient is counted as a patient with rescue medication use. The use of rescue medication will be analyzed with a logistic regression model with treatment group, baseline ARR and geographical region as*

*covariates. The odds ratio, corresponding 95% CI, and p value for the treatment group will be reported. This analysis is conducted for the double-blind period.*

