##### **4.3.2.1 Satralizumab and Placebo: Double-blind Period**

The patient will receive an SC injection of satralizumab or placebo at Weeks 0, 2 and 4, and Q4W thereafter during the double-blind period. The double-blind period ends when either the patient has a relapse or the total number of protocol-defined relapses judged by the CEC reaches 26.

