##### 4.4.1 Major Permitted Therapies for NMO

##### **Permitted Medication/Therapy During the Double-Blind Period**

###### 1. Baseline treatment

One of the drugs listed below is required as monotherapy for baseline treatment at baseline. A dose must not exceed the dose defined below and a stable dose must be maintained. Dose decrease is permitted only for safety reasons. Dose increase or change of baseline treatment is not permitted.

- Azathioprine\*: 3 mg/kg/day
- Mycophenolate mofetil\*: 3000 mg/day
- Oral corticosteroids: 15 mg/day (prednisolone equivalent)

\* Combination with oral corticosteroids (15 mg/day [prednisolone equivalent]) is permitted in patients aged 12 to 17 years at the time of informed consent.

2. Rescue therapy for clinical relapse (leads to end of the double-blind period); pulse IV corticosteroids, intravenous immunoglobulin (IVIG), and/or apheresis (including plasma exchange and plasmapheresis).

Rescue therapy should proceed at the discretion of the treating Investigator after the examining assessor has completed EDSS/FSS assessment at extra visit at relapsing (except in case of emergency when urgent treatment is required before the patient can undergo this assessment).

3. Pain medications (including but not limited to pregabalin, gabapentin, carbamazepine, clonazepam, duloxetine, tramadol/acetaminophen).

Starting of pain medications is permitted, however the dose should be stable during the double-blind period. In case pain control is insufficient, dose increase or change of pain medication is permitted. Dose decrease and temporary treatment suspension are permitted for only safety reasons.

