5.2 General Presentation Considerations

Unless otherwise specified, Week 0 (Day 1) visit, which in most cases should correspond to the date of first dose, will be the baseline in the double-blind period, in which the baseline measurements will be collected at Day 1 prior to the first injection.

The date of first SA237 dose will be the baseline in the All-Subjects-Treated (All SA237) population analyses, in which the baseline measurements will be collected on the day of the first dose, prior to the study drug injection.

The definition of each duration for analysis is as follows:

- Double blind period for efficacy analysis
 - Double-blind period starts on the day of the randomization. The double-blind period ends on the earliest day of 1) clinical cutoff date (CCOD), 2) the day before the first

treatment in the extension period, 3) the end of the study, or 4) last contact for patients lost to follow up.

- Double blind period for safety analysis
 - Double blind period starts on the day of first dose of study drug. The double-blind period ends on the same day as efficacy analysis..
- SA237 exposure duration for safety analysis (for All SA237 analysis)
 - SA237 exposure duration starts on the day of first dose of SA237. SA237 exposure duration ends on the earliest day of 1) CCOD, 2) the end of the study, or 3) last contact for patients lost to follow up.

The definition of summaries by visit is as follows:

- Summaries by visit for double blind period
 - Baseline is defined as the latest data before the date of first administration for all data. Summarized visits except for baseline are defined as follows. Irregular visits such as unscheduled visit between week X, dose outside the visit window (DOW), extra visit at relapsing, and the end of the study are out of scope. Week X visits are directly used for categories of time. In other words, time window is not applied. If there are the same visits data, one representative assessment nearest to the scheduled visit day will be summarized.
- Summaries by visit for All SA237 analysis

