- Analysis of TFR (treated clinical relapse: optic neuritis) will be performed using the stratified log-rank test.
- Analysis of TFR (clinical relapse) will be performed using the stratified Cox regression.
- Analysis of TFR (treated clinical relapse) will be performed using the stratified Cox regression.
- Analysis of TFR (treated clinical relapse: optic neuritis) will be performed using the stratified Cox regression.

- Analysis of TFR (protocol-defined relapse based on CEC adjudication (regardless of assessment limit of 7 days)) will be performed using the stratified Cox regression.
- Analysis of TFR (protocol-defined relapse based on EDSS/FSS increase relative to baseline) will be performed using the stratified Cox regression.
- TFR (clinical relapse) is defined if the relapse will be reported in eCRF. TFR (treated clinical relapse) is defined if the subject received rescue therapy for clinical relapse.
- A by-subject listing of TFR, which also includes clinical relapse, treated clinical relapse, treated clinical relapse: optic neuritis, will be provided.

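### Rescue use in the double-blind period is compared by logistic regression with no allowance for time at risk, so the odds ratio depends on how long patients happened to be followed

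*Protocol*

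**What the plan says.** The paragraph on use of rescue medication in Protocol Section 6.5.2 codes each patient yes or no: "If a patient has at least one treated clinical relapse, then this patient is counted as a patient with rescue medication use". It continues "The use of rescue medication will be analyzed with a logistic regression model", with treatment, baseline ARR and region as covariates, and asks for an odds ratio, confidence interval and p value. On scope it says "This analysis is conducted for the double-blind period". It gives no exposure term, no fixed time point and no rule for patients who leave early.

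That period has no fixed length. Protocol Section 4.3.2.1 says "The double-blind period ends when either the patient has a relapse or the total number of protocol-defined relapses judged by the CEC reaches 26". Section 4.4.1 lists "Rescue therapy for clinical relapse (leads to end of the double-blind period"). Section 4.5.3.3 takes a patient out of the period once the CEC confirms a relapse, whether or not rescue was given. SAP Section 5.2 ends the efficacy period at the earliest of the clinical cut-off, the day before the first extension dose, the end of the study, and last contact.

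Elsewhere the plan does allow for time. SAP Section 5.10.3.2 puts a log-exposure offset in the ARR model. SAP Section 1 records that the logistic analysis of relapse-free subjects was dropped because of many early events. SAP Section 5.10.2 includes a neighbouring time-to-event analysis: "Analysis of TFR (treated clinical relapse) will be performed using the stratified Cox regression", with a log-rank test and Kaplan-Meier output.

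**The concern.** A yes/no outcome compared without regard to time is easiest to interpret when everyone is observed for the same period. Here a patient lost after one month without rescue and one followed for two years without rescue enter the model identically. Three things follow.

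- The odds ratio has no fixed target. Even with a constant treatment effect on the hazard, its value moves with the length of follow-up.
- The timing of rescue is discarded, which costs some power.
- If leaving without rescue differed between the arms, the odds ratio would move away from 1 with no drug effect at all.

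At stake is a reported treatment p value and odds ratio for a supplementary outcome. The primary and key secondary tests are not involved.

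**Working it through.** **Inputs from the documents** (Protocol Section 6.2, SAP Section 5.14): 35 patients per arm; placebo hazard 0.4184 per year; hazard ratio 0.335, so the active hazard is 0.4184 × 0.335 = 0.1402; accrual over one year plus 1.5 years, so planned follow-up of 1.5 to 2.5 years; 10% dropout at two years, a hazard of −ln(0.9)/2 = 0.0527 per year; 26 events.

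**Assumptions.** The documents give no rescue rate. Rescue is taken to follow the design relapse hazards, either for every relapse or for 85% of them.

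**1. The plan's own figure.** Schoenfeld: 4(1.960 + 0.842)² / (ln 0.335)² = 26.25, against 26 in the plan; 26 events give 79.6% power. With uniform accrual the expected count is 27.0 (18.9 placebo, 8.1 active). The design inputs are reproduced.

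**2. Odds ratio against follow-up, constant hazard ratio, no dropout.** The event probability by time T is 1 − exp(−hT), so the odds are exp(hT) − 1 and

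OR(T) = [exp(0.1402T) − 1] / [exp(0.4184T) − 1].

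| T (years) | Placebo | Active | OR |
|---|---|---|---|
| 0.5 | 0.189 | 0.068 | 0.312 |
| 1.0 | 0.342 | 0.131 | 0.290 |
| 1.5 | 0.466 | 0.190 | 0.268 |
| 2.0 | 0.567 | 0.244 | 0.247 |
| 2.5 | 0.649 | 0.296 | 0.227 |

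**3. Planned mix of follow-up.** With dropout hazard e, p = h/(h+e) × [1 − exp(−(h+e)T)]. Averaged over T from 1.5 to 2.5 years, this gives 53.9% on placebo and 23.2% on active, so OR = (0.232/0.768)/(0.539/0.461) = 0.258. About 6% of patients leave event-free before 1.5 years and would be coded as non-users.

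**4. Equal dropout, simulated** (unadjusted logistic Wald test against unstratified log-rank).

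- All relapses rescued, calendar cut-off at 2.5 years: power 78.9% log-rank and 74.0% logistic. With no drug effect, logistic rejects in 4.3% of trials and the median OR is 1.00.
- 85% rescued, cut-off at the 26th relapse: power about 69% log-rank and 65% logistic, with no inflation of the logistic test.

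**5. Unequal dropout, no drug effect** (the rates are assumed).

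- From the formula in step 3, with 5.13% per year in the other arm: active at 15% per year gives OR 0.83, active at 30% gives 0.63, and placebo at 30% gives 1.60.
- Simulated logistic rejection is 7.2% at 5% against 20% per year and 14.8% at 5% against 30% per year. Log-rank stays at 5.0 to 5.4%.
- A milder contrast, 30% on placebo against 10% on active over two years with 85% rescued, gives a median OR of about 1.14 with rejection still near 5%.

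**6. The neighbouring SAP analysis.** Section 5.10.2 describes TFR (treated clinical relapse) twice. The paragraph introducing the sensitivity analyses counts rescue-treated relapses together with protocol-defined relapses. The list that follows defines the event by receipt of rescue therapy for a clinical relapse. On the second definition it is time to first rescue, apart from also censoring at a switch or increase of baseline treatment. On the first it is a wider event that includes untreated protocol-defined relapses.

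**The case against.** The strongest reply is that a time-to-event analysis of nearly this outcome is already planned, so the logistic model is only a descriptive supplement. This largely stands if the SAP's rescue-only definition governs. It does not settle the matter, because the SAP gives two definitions and the Protocol still asks for a p value from the logistic model.

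A second reply is that randomisation balances follow-up. With equal dropout this also stands: the test keeps its size and the cost is four or five points of power. The plan assumes a single dropout rate, and material distortion needs large contrasts that no document figure supports.

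Third, log-rank and Cox need non-informative censoring. Censoring a patient who leaves after an untreated CEC-confirmed relapse could well be informative, so the replacement is not assumption-free.

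Two stronger readings are tempting. A reader might infer that follow-up ending at rescue is what misclassifies patients. It is not: rescued patients are counted as users, and the difficulty lies with those whose follow-up ends without rescue. A reader might also infer bias from the shorter mean placebo follow-up expected under the design (about 1.25 against 1.58 years in simulation). That gap arises with equal dropout because placebo patients relapse sooner. It reflects the treatment effect and is not evidence of confounding.

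**Conclusion.** The point holds as a weakness of the chosen analysis. The logistic model ignores unequal time at risk, so its odds ratio is tied to follow-up length: 0.31 to 0.23 over 0.5 to 2.5 years at a constant hazard ratio of 0.335. With equal dropout the further cost is modest, about 69% against 65% power if 85% of relapses are rescued, or 78.9% against 74.0% if all are. These figures rest on exponential times, independent dropout and rescue following the design relapse hazards.

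The documents do not support the claim that the comparison is biased. That would need leaving to differ materially by arm, which is an assumption. Nor do they support a threat to the trial's conclusion: rescue use is in no endpoint list and lies outside the testing sequence of Protocol Section 6.5.2 and SAP Section 5.10.1.4. A change is worth making because it is cheap and because the plan already allows for exposure in its ARR model.

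**What to change.** - In Protocol Section 6.5.2, make the inferential analysis time from randomisation to first rescue therapy in the double-blind period. Use the stratified log-rank test and stratified Cox model already coded in SAP Section 7.7, with Kaplan-Meier rescue-free rates. Censor patients without rescue at the end of their double-blind follow-up as defined in SAP Section 5.2. Keep any odds ratio as descriptive, without a p value.
- In SAP Section 5.10.2, reconcile the two definitions of TFR (treated clinical relapse). If the event is receipt of rescue, that analysis can nearly serve as the replacement and Section 6.5.2 can point to it.
- State how the analysis handles patients who leave after a CEC-confirmed relapse that was not treated with rescue, and add a sensitivity analysis, for example counting those exits as events.
- Label the analysis as specified after the double-blind period. The rescue paragraph is printed in italics, which the Protocol uses for new information, and Section 1.3 says that period is complete.

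The cost is a few sentences. Rescue start dates are already collected (Protocol Section 4.4) and the model code exists. The downside is small: changing a model after results are available must be disclosed.

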### **6.5.3 Further Analysis**

#### **6.5.3.1 Sensitivity Analysis for Primary Endpoint**

Several sensitivity analyses are planned for the primary efficacy analysis of TFR to account for the potential impact of differences in definition of primary endpoint. In this analysis the following populations will be analyzed for TFR:

- Patients with clinical relapse
- Patients with treated clinical relapse
- Patients with treated clinical relapse: Optic Neuritis
- Patients with protocol-defined relapse based on CEC adjudication (regardless of assessment limit of seven days)
- Patients with protocol-defined relapse based on EDSS/FSS increase relative to baseline

Further details will be mentioned in the SAP.

#### **6.5.3.2 Sensitivity Analysis for Key Secondary Endpoint**

Several sensitivity analyses are planned for the key secondary efficacy analysis of VAS for pain and FACIT fatigue to account for the potential impact of differences in handling of missing data. In this analysis the following analyses will be conducted:

- The change in VAS for pain score from baseline to Week 24 in the double-blind period will be analyzed by ANCOVA method with hot-deck imputation
- The change in FACIT fatigue scale score from baseline to Week 24 in the double-blind period will be analyzed by ANCOVA method with hot-deck imputation

Further details will be mentioned in the SAP.

#### **6.5.3.3 Subgroup Analysis**

The subgroup summary tables for TFR will be presented by AQP4Ab status at screening (positive/negative) in NMO and NMO/NMOSD. In case that satralizumab does not show the effectiveness in NMO patients with AQP4Ab negative at all, companion diagnostics co-development will be considered by using this data. The subgroup analysis for adolescent will also be conducted.

Further details will be described in the SAP.

### Adolescents:

Summary statistics will be provided for efficacy outcome measures. Outcome measures will be reported for all adolescents who are enrolled into this study, as well as for all adolescents who are randomized into the double-blind period. Separate listings for adolescents who are enrolled into the extension period will be provided, as appropriate.

## **6.6 SAFETY ANALYSES**

All safety analyses will be performed on the SAF. Safety variables to be assessed are AEs, AESIs, SAEs, selected AEs, injection site reactions, patient withdrawals due to AEs, change in 12-lead ECGs, measurements of laboratory parameters, and vital signs (including body weight).

Summary tables for number and percentage of patients with adverse drug reactions (i.e., AEs related to study drug) will be tabulated.

Adverse events will be summarized by System Organ Class and preferred term, based on Medical Dictionary for Regulatory Activities coding, and grade of severity. The incidence of treatment emergent AEs will also be displayed by severity and relationship to the study drug, respectively. In addition, the incidence of AEs leading to withdrawal from treatment and SAEs will be tabulated.

Incidence of Selected AEs (see Section 5.2.4) will be tabulated. IRRs will be further analyzed according to whether they meet Sampson's criteria for diagnosis of anaphylaxis (Sampson et al, 2006).

Laboratory values (including hematology, blood chemistry, and urinalysis), frequencies of laboratory abnormalities, vital signs (temperature, SBP, DBP and pulse rate), physical examination, 12-lead ECG, and suicidality (C-SSRS) will be summarized. Measurement and change from Baseline in continuous laboratory parameters (hematology, clinical chemistry, and urinalysis), continuous ECG, vital signs (blood pressures and pulse rate), and body weight will be summarized using descriptive statistics. When analyzing categorical data, the number and percentage of patients in each category will be presented. In addition, shift tables may be used to evaluate the number and percentage of patients having a different post-baseline status when compared to their baseline status. Numbers of patients who meet the marked abnormality criteria will also be presented.

### Adolescents:

Safety outcome measures will be summarized. Summaries will be reported for all adolescents who are enrolled into this study, as well as for all adolescents who are randomized into the double-blind period. Separate listings for adolescents who are enrolled into the extension period will be provided, as appropriate.

## **6.7 PHARMACOKINETIC/PHARMACODYNAMICS ANALYSES**

Descriptive statistics, such as geometric mean, geometric coefficient of variance (CV) and the 95% CI for the geometric mean for the serum satralizumab concentration, as well as arithmetic mean, SD, median, minimum, and maximum on the measured serum satralizumab concentration, IL-6, sIL-6R, anti-AQP4Ab and plasmablasts will be calculated by visit and per defined time window post-dose for the PK-PPS.

An exploratory analysis to identify any potential relationship among serum satralizumab concentration and PD (CRP, IL-6, sIL-6R, plasmablasts and anti-AQP4Ab) will be performed. These results will be described and reported in the clinical study report.

In addition, nonlinear mixed-effects modeling will be used to analyze the sparse sampling dose-concentration-time data of satralizumab. The data from this study will be pooled with data from SA-001JP study and SA-105JP study to develop a population PK model for satralizumab. A covariate analysis will be conducted to evaluate the effect of covariates on satralizumab exposure. Some covariates such as body weight, age and gender will be included in the covariate analysis. Population and individual estimates of primary PK parameters [e.g., clearance (CL/F), distribution volume (V/F)] and secondary PK parameters [e.g., area under the serum concentration-time curve (AUC), average trough serum concentration ( $C_{\text{trough}}$ )] will be computed.

Details of this mixed-effects modeling analysis and the results will be described and reported in a document separated from the clinical study report.

